3. INVESTIGATIONAL PLAN

3.1. Study Design

This is a phase 1/2 open-label study assessing the safety, reactogenicity, and immunogenicity of saRNA COVID-19 boost vaccines in participants that have been previously vaccinated against or previously infected with COVID-19. Participants enrolled will include individuals previously vaccinated against COVID-19 or previously infected with COVID-19 > 3 months prior to enrollment. Previously unvaccinated/vaccinated status and previously uninfected/infected status will be established by medical history and by SARS-CoV-2 serology assessed in the prescreening visit.

The phase 1 study is a single arm, open-label study. The phase 2 is a randomized open-label study. For the phase 2 study, laboratory analyses of immunogenicity assessments will be performed blind to participants' vaccine treatment on study. In all study phases, SARS-CoV-2 serological status will be assessed in a prescreening visit.

Participants will be ≥ 18 years of age who are healthy or have medically-stable chronic diseases. The treatment regime is described in the sections that follow. The study schema is shown in [Figure 1](#).

Phase 1

In the phase 1 study, up to 60 previously vaccinated/infected participants will be enrolled in 6 separate cohorts to receive a single vaccine boost consisting of either the AAHI-SC2 or AAHI-SC3 vaccine. Dosing schedule, mode of administration, and dosage for phase 1 are indicated in [Table 4](#).

Table 4: Phase 1 Previously Vaccinated/Infected Dosing Schedule

Phase	Cohort	Participants	Vaccine	Dosing Schedule	Dosage
PHASE 1	1A	10	AAHI-SC2	Day 1	25 μ g IM
	1B	10	AAHI-SC2	Day 1	50 μ g IM
	1C	10	AAHI-SC2	Day 1	70 μ g IM
	2A	10	AAHI-SC3	Day 1	25 μ g IM
	2B	10	AAHI-SC3	Day 1	50 μ g IM
	2C	10	AAHI-SC3	Day 1	85 μ g IM

Safety will be assessed for all participants and will include monitoring of vital signs, and incidence and severity of AEs. Blood samples will be collected for hematology and chemistry analyses and urine samples will be collected for urinalysis. Toxicities will be graded using the

Guidance for Industry: Toxicity Grading Scale for Healthy Adult and Adolescent Volunteers Enrolled in Preventive Vaccine Clinical Trials (2007).

For each cohort in phase 1, after all 10 participants have completed the toxicity assessment period, the SRC will review safety results to determine if the event warrants stopping the trial, modifying the trial, or continuing without modification.

Solicited local and systemic reactogenicity AEs will be collected using diaries for 7 days following study intervention (ie, administration of vaccine). Unsolicited AEs will be recorded in a diary from time of vaccination until 30 days after study intervention. Medically attended adverse events (MAAEs) and SAEs will be recorded for 6 months after study intervention (related MAAEs and SAEs will be recorded at any time).

Immunogenicity analyses will be conducted by collecting serum and PBMC samples from individual participants before and after vaccinations to test for humoral- and cell-mediated immune responses. Neutralizing antibodies will be assessed.

Phase 2

In the phase 2 study, up to 120 previously vaccinated/infected additional participants will be enrolled. Participants in phase 2 will be randomized 1:1:1:1 to receive Janssen or Pfizer-BioNTech vaccine (control arm), the AAHI SC2 vaccine (experimental arm 1), or the AAHI-SC3 vaccine (experimental arms 2 and 3). Dose levels for the AAHI-SC2 and AAHI-SC3 vaccines will be as determined in the phase 1 study. Randomization will be stratified by age (18 to 55 years or > 55 years), by previous infection (previously infected or not), and by HIV status (positive or negative). Treatment arms are shown in Table 5.

Table 5: Phase 2 Previously Vaccinated/Infected Dosing Schedule

Treatment Arm	Participants	Vaccine	Dosing schedule	Dosage
Control arm	30	EUA or approved vaccine	Day 1	Per prescribing information
Experimental arm 1	30	AAHI-SC2	Day 1	TBD: As determined in phase 1 study
Experimental arm 2	30	AAHI-SC3	Day 1	TBD: As determined in phase 1 study
Experimental arm 3	30	AAHI-SC3	Day 1 and day 29	TBD: As determined in phase 1 study

In addition to dosing visits described above, all participants in all phases of the study will have follow up study visits for data collection.

The SRC will provide ongoing safety review in the phase 2 study. If a possible safety signal is detected, the SRC will determine if the event warrants stopping the trial, modifying the trial, or continuing without modification.

Solicited local and systemic reactogenicity AEs will be collected using diaries for 7 days following study intervention (ie, administration of vaccine). Unsolicited AEs will be recorded in

a diary from time of vaccination until 30 days after study intervention. MAAEs and SAEs will be recorded for 6 months after study intervention (related MAAEs and SAEs will be recorded at any time).

Immunogenicity analyses will be conducted by collecting serum and PBMC samples from individual participants before and after vaccinations to test for humoral- and cell-mediated immune responses. Neutralizing antibodies will be assessed.

3.2. Number of Participants

Initially up to 180 participants will be enrolled in this study (60 participants in phase 1, and 120 participants in phase 2).

3.3. Duration of Study

3.3.1. Duration of Treatment

For most participants, treatment will be confined to study day 1. For participants in experimental arm 3 of the phase 2 study, treatment will occur on day 1 and day 29.

3.3.2. Duration of Follow-Up

Participants who receive study treatment will be followed by a health care professional until either death (by any cause) or for 1 year past first administration of vaccine.

3.3.3. End of Study

The end of study is defined as either the date of the last visit of the last participant to complete the post-treatment follow-up, or the date of receipt of the last data point from the last participant that is required for primary, and/or secondary analysis, as specified in the protocol statistical analysis plan (SAP), whichever is the later date.

3.4. Study Endpoints

3.4.1. Phase 1

3.4.1.1. Primary Endpoints

- Incidence of MAAEs and SAEs through 1 week post final vaccine administration
- Incidence of MAAEs and SAEs through 30 days post final vaccine administration
- Incidence of MAAEs and SAEs through 6 months post final vaccine administration
- Incidence and severity of solicited local reactogenicity AEs through 1 week after each vaccine administration
- Incidence and severity of solicited systemic reactogenicity AEs through 1 week after each vaccine administration
- Incidence and severity of unsolicited AEs through 1 week post final vaccine administration

- Incidence and severity of unsolicited AEs through 30 days post final vaccine administration
- Incidence of abnormal changes of laboratory safety examinations
- Changes in vital signs

3.4.1.2. Secondary Endpoints

Humoral Immunogenicity:

- GMT of S-specific and N-specific IgG antibodies against 2019 novel coronavirus tested by ELISA in serum
- GMT of neutralizing antibody

Cellular Immunogenicity:

- T cell activity against SARS-CoV-2 S protein and N protein as assayed by ELISpot

3.4.2. Phase 2

3.4.2.1. Primary Endpoints

Humoral Immunogenicity:

- GMT of S-specific and N-specific IgG antibodies against 2019 novel coronavirus tested by ELISA in serum
- GMT of neutralizing antibody

Cellular Immunogenicity:

- T cell activity against SARS-CoV-2 S protein and N protein as assayed by ELISpot

3.4.2.2. Secondary Endpoints

3.4.2.2.1. Safety

- Incidence of MAAEs and SAEs through 30 days post final vaccine administration
- Incidence of MAAEs and SAEs through 6 months post final vaccine administration
- Incidence and severity of solicited local reactogenicity AEs through 1 week after each vaccine administration
- Incidence and severity of solicited systemic reactogenicity AEs through 1 week after each vaccine administration
- Incidence and severity of unsolicited AEs through 30 days post final vaccine administration

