6.3. Safety Assessments

All participants will be monitored for AEs during the study. Assessment of AEs will include the following parameters:

- All MAAEs and SAEs for 6 months after last vaccine administration (related MAAEs and SAEs at any time)
- Solicited local and systemic AEs via diary for 7 days after each vaccine administration (applicable to the phase 1 and phase 2 studies)
- Unsolicited AEs via diary from first dose of study treatment until 30 days after last vaccination (applicable to the phase 1 and phase 2 studies)
- Vital signs
- Body weight
- Physical examinations
- Hematology: CBC with differential
- Chemistry panel: Collection of whole blood for complete metabolic panel (CMP)
- Urinalysis: protein, glucose, and RBCs
- Pregnancy test.

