Laboratory Assessments											

Study Period	Prescreening ^a	Baseline/ Screening	Vaccine Administration and Initial Follow-Up						Extended Follow-Up		
			1	8	22	29	36	60	180	365	
Study Day	-5 to -1	-5 to -1	1	8	22	29	36	60	180	365	
Clinic visit number	Prescreening	Screening	1	2	3	4		5	6	7	
Windows (Days)			± 3						± 7	± 14	
Chemistry panel ^h		X				X					
Hematology ⁱ		X				X					
Urinalysis ^j		X				X					
Biospecimens for SARS-CoV-2 ^k		X	X		X	X					
Collect whole blood for immunogenicity ^l			X	X					X		
Pregnancy test ^m		X	X				X				
Collect blood for SARS-CoV-2 serology	X										
HIV testing ⁿ	X										

^a If possible, the prescreening visit should occur on the same day as and immediately prior to the screening visit.

^b A TB symptom screening questionnaire per local guidelines will be used. If screening positive on questionnaire then sputum test and chest X-ray may be done to exclude the diagnosis of TB. If TB is excluded on these tests and the investigator considers that further TB testing is not clinically indicated then the potential participant may proceed with enrollment into the study. All potential participants suspected of having or with proven TB will be linked into care at their local clinic.

^c Potential exposure to SARS-CoV-2, symptoms of COVID-19, and outside testing results for SARS-CoV-2 infection will be collected at each assessment.

^d Physical examination will be performed at screening and symptom-directed (targeted) physical examination at all other time points if indicated. Height required at baseline/screening visit only.

^e Vital signs of temperature, heart rate, blood pressure, and respiratory rate will be assessed as indicated. Temperature will be documented at each visit and subsequently if clinically indicated.

^f Solicited AE diaries will be issued on day 29 and collected on day 60 only for participants in experimental arm 3 of the phase 2 study.

^g The telephone follow-up on day 36 is required only for participants in experimental arm 3 of phase 2 that get a boost on day 29.

^h See Table 9 for information on chemistry laboratory assessments.

ⁱ Hematology to include CBC with differential (5 part).

^j Urinalysis testing will include at a minimum protein, glucose, and presence of red blood cells. Sample collection should occur prior to vaccine administration.

^k Sample collection should occur prior to vaccine administration.

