7.2. Definition of Adverse Events

AEs and grading criteria listed below are consistent in definitions in 21 CFR 312.32.

An AE is any noxious, unintended, or untoward medical occurrence that may appear or worsen in a participant during the study. It may be a new intercurrent illness, a worsening concomitant illness, an injury, or any concomitant impairment of the participant's health, including laboratory test values (as specified by the criteria below), regardless of etiology. A diagnosis or syndrome should be recorded on the AE page of the case report form (CRF) rather than the individual signs or symptoms of the diagnosis or syndrome.

An abnormal laboratory value is considered to be an AE if the abnormality:

- Results in discontinuation from the study;
- Requires treatment, modification/interruption of the study treatment dose, or any other therapeutic intervention; or
- Is judged to be of significant clinical importance.

Regardless of the severity grade, only laboratory abnormalities that fulfill a seriousness criterion need to be documented as an SAE.

If a laboratory abnormality is one component of a diagnosis or syndrome, then only the diagnosis or syndrome should be recorded as an AE. If the abnormality was not a part of a diagnosis or syndrome, then the laboratory abnormality should be recorded as an AE.

An AE with medically-attended visits (either in person or telemedicine visit) that are not routine visits for physical examination or vaccination, such as visits for hospitalization, an emergency room visit, or an otherwise unscheduled visit to or from medical personnel (medical doctor) for any reason, will be documented as a MAAE. MAAEs can also be SAEs and will follow the same serious adverse event criteria and collection guidelines noted in [Section 7.3](#).

Duration and Frequency for Collecting AE and SAE Information

In the phase 1 and phase 2 studies, solicited AEs will be recorded by the investigator for 7 days after each dose. In the phase 1 and phase 2 studies, unsolicited AEs will be recorded from the time of first dose of study treatment until 30 days after study intervention. All MAAEs and SAEs will be recorded by the investigator from the time of first dose of study treatment until 6 months after study intervention. For MAAEs/SAEs that are considered related to study treatment, those events should be reported at any time regardless of vaccine administration date or end of study visit date.

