8.3. Statistical Methods

8.3.1. General Approach

The purpose of this phase 1/2 study is to determine the safety, reactogenicity, and immunogenicity of saRNA COVID-19 boost vaccines in participants that have been previously vaccinated against or previously infected with COVID-19. Participants enrolled will include individuals previously vaccinated against COVID-19 or previously infected with COVID-19 > 3 months prior to enrollment. The phase 1 study is a single arm, open-label study. The phase 2 is a randomized open-label study. For the phase 2 study, laboratory analyses of immunogenicity assessments will be performed blind to participants' vaccine treatment on study. Results for phase 1 will be summarized by cohort and results for phase 2 will be summarized for each randomized arm.

Descriptive statistics will be presented for all study endpoints. Continuous variables will be summarized as mean, median, standard deviation, and minimum and maximum values.

Categorical variables will be summarized as the number and percentage of participants in each category. Data from all investigational sites will be pooled in the analyses and summary tables.

No statistical comparisons of the phase 2 arms is planned. Subgroup analyses providing descriptive statistics for the various randomization strata levels may be performed depending on the number of participant's in each strata. Details of the subgroup analyses will be provided in the Statistical Analysis Plan.

Data for participants who are screen failures will not be included in the study database or in any analyses or summary tables.

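### Phase 2 unsolicited AEs and 30-day MAAEs/SAEs are counted over 58 days in two-dose arm 3 but 30 days in the single-dose arms, so the per-arm percentages are not comparable

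*Combined protocol and SAP*

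**What the plan says.** Section 3.4.2.2.1 lists three phase 2 safety endpoints whose end is tied to the last dose: "Incidence and severity of unsolicited AEs through 30 days post final vaccine administration", "Incidence of MAAEs and SAEs through 30 days post final vaccine administration" and "Incidence of MAAEs and SAEs through 6 months post final vaccine administration".

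The start is tied to the first dose. Section 6.3 collects "Unsolicited AEs via diary from first dose of study treatment until 30 days after last vaccination", and the Appendix 2 diary instructions match it. Section 7.2 records MAAEs and SAEs "from the time of first dose of study treatment until 6 months after study intervention".

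The number of doses differs by arm. Section 3.3.1 says: "For participants in experimental arm 3 of the phase 2 study, treatment will occur on day 1 and day 29". The control arm and experimental arms 1 and 2 receive one dose, on day 1 (Table 5).

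On reporting, section 8.3.1 says that "results for phase 2 will be summarized for each randomized arm", with categorical variables given as number and percentage of participants. It also says that no statistical comparison of the phase 2 arms is planned. Section 8.3.2 refers only to a time period of interest. The text gives no common window across arms, no per-dose window for unsolicited AEs and no rate per unit of follow-up. The solicited AE endpoints, by contrast, are defined for one week after each administration.

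**The concern.** A cumulative percentage depends on how long participants are watched. Here the start is the same in every arm but the end moves with the last dose, so the two-dose arm is watched for longer by construction. Background illness alone will then tend to put more arm 3 participants in the table.

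Arm 3 differs from arm 2 by a second AAHI-SC3 dose, so a reader will look at these columns to judge what that dose adds in unsolicited AEs, MAAEs and SAEs. As defined, the columns mix any effect of the second dose with nearly twice the observation time. With no model or test in the plan, the window definition is the only place where the difference in follow-up can be handled.

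**Working it through.** **Inputs from the documents.** First dose on day 1 in all arms; final dose on day 29 in arm 3 and day 1 elsewhere (sections 3.1 and 3.3.1). Window end is 30 days or 6 months after the final dose (3.4.2.2.1). There are 30 participants per arm (8.4, 8.5). The plan states no window length in days and no expected AE rate, so there is no figure of its own to reproduce.

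**Window length, 30-day endpoints** (elapsed days = final dose day + 30 − 1):
- Single-dose arms: 1 + 30 − 1 = 30 days, ending on day 31.
- Arm 3: 29 + 30 − 1 = 58 days, ending on day 59.
- Ratio: 58/30 = 1.93. Counting calendar days inclusively gives 59/31 = 1.90.
- If the day-29 visit can move by 3 days (an assumed reading of the Table 10 windows row, which is broken in the text), arm 3 has 55 to 61 days and the ratio is 1.83 to 2.03.

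**Expected incidence with no vaccine effect.** Assume a constant background hazard and a 30-day incidence p. The documents give no p, so a range is shown. Arm 3 incidence = 1 − (1 − p)^(58/30). The last two columns are exact binomial probabilities that more participants are affected in arm 3 than in control, with 30 per arm.

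| Assumed p | Arm 3 | Expected counts of 30 | P(arm 3 > control) | Same, equal windows |
|---|---|---|---|---|
| 5% | 9.4% | 1.5 vs 2.8 | 66% | 38% |
| 10% | 18.4% | 3.0 vs 5.5 | 78% | 41% |
| 20% | 35.0% | 6.0 vs 10.5 | 88% | 44% |
| 30% | 49.8% | 9.0 vs 14.9 | 93% | 44% |

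Example: 1 − 0.80^1.933 = 1 − 0.650 = 0.350, and 0.350/0.20 = 1.75.

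**Window length, 6-month endpoint.** Taking 6 months as 180 days, arm 3 has 180 + 28 = 208 days and the ratio is 208/180 = 1.16. An assumed 20% becomes 1 − 0.80^(208/180) = 22.7%, or 6.0 against 6.8 participants of 30.

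**Solicited AEs.** Each window is 7 days after each dose, so the final-dose wording does not lengthen it.

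**Effect of a common window.** With the same start and end day in every arm, the exponent is 1 and the expected ratio under the same assumptions is 1.00.

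**The case against.** The case against giving this much weight has several parts.

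- *Regimen-level incidence is legitimate.* A two-dose course takes longer, and what happens from its start to 30 days after its end is a fair question. That stands, and is why the present tables should be kept. It does not make the column comparable with a single-dose column.
- *These are secondary, descriptive endpoints.* No arm comparison is tested, the sample size has no statistical basis, and no stated decision rule uses the contrast. That stands: a reader might infer an inflated error rate, but there is no test whose error rate could be inflated.
- *Section 8.1 defers detail to a SAP.* A common window may be set there. The available text contains no such rule, and the endpoint wording points the other way.
- *The data can be repaired.* Section 7.4.3 records start and stop dates for all AEs, so tables on other windows can be produced. This stands, and makes the fix cheap.

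Some stronger readings are tempting but are not supported:

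- A reader might infer that nothing is recorded in the single-dose arms while arm 3 is in its post-dose-2 period. That is wrong for MAAEs and SAEs, which every arm records for 6 months. For unsolicited AEs it is unclear: section 6.3 and Appendix 2 end recording 30 days after the last dose, but Table 10 appears to show AE and unsolicited-diary collection at day 60 with no restriction to arm 3.
- A reader might infer that this is the trial's only safety contrast between one and two doses. Solicited AEs are also summarised by arm and are unaffected.
- Table 10 footnote g says: "The telephone follow-up on day 36 is required only for participants in experimental arm 3". A reader might infer that this call inflates arm 3 further. It falls 7 days after dose 2, as the day-8 visit does after dose 1, and nothing in the documents allows its effect to be sized.

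**Conclusion.** The point holds for unsolicited AEs and for the 30-day MAAE/SAE endpoint. Arm 3 is observed for 58 elapsed days against 30, and its percentages cannot be read beside the other arms. For assumed background incidences of 10% to 30%, the excess expected from follow-up alone is about 8 to 20 percentage points. That is an expectation, not a certainty: with 30 per arm, arm 3 would fail to exceed control about 34% of the time at 5% background and 22% at 10%.

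The 6-month MAAE/SAE endpoint has the same structure but only about 16% more time, and it should not be put on a level with the 30-day endpoints.

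The figures assume a constant background hazard, no vaccine effect, dose 2 given on day 29 to all of arm 3, and complete follow-up. The background rates are assumed because the documents give none. The consequence is a misleading descriptive table. It should be corrected before the phase 2 tables are specified.

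**What to change.** Amend sections 3.4.2.2.1 and 8.3.2, using data already collected:

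1. Report unsolicited AEs and MAAEs/SAEs for all four arms over a common window from day 1 to before the day-29 visit.
2. For arm 3, report events after dose 1 and after dose 2 separately, with person-time rates beside the percentages. Rates alone are not enough: if events cluster soon after a dose, averaging over unequal follow-up still distorts the comparison.
3. Report MAAEs/SAEs in all arms from day 1 to day 59 and from day 1 to day 180. Every arm already records them for that long.
4. Keep the tables that run to 30 days or 6 months after the final dose as additional displays, with the length of follow-up shown for each arm.

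Reconcile section 6.3 and Appendix 2, where unsolicited recording ends 30 days after the last dose, with Table 10, which appears to place AE and unsolicited-diary collection at day 60 for every arm. If unsolicited AEs are recorded to day 60 in all arms, add a common day-29-to-day-59 window, which gives the post-dose-2 period a concurrent comparator.

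Items 1 to 4 cost endpoint and analysis wording plus extra tables, with no new data collection. Extending the diary in the single-dose arms is optional. It would mean about 4 more weeks of daily diary for 90 participants (3 × 30) and a protocol amendment, with re-consent if the consent content changes.
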